7.3 Statistical Inference (Estimation or Hypothesis[es])

No formal hypothesis will be tested. Instead, point estimates and 95% confidence intervals will be derived to determine the rate of hypocalcemia following cinacalcet initiation, rate of cinacalcet discontinuation following hypocalcemia event and rate of cinacalcet re-initiation following discontinuation due to hypocalcemia. In addition, hazard ratios and 95% confidence intervals will be carried out for the predictor analyses.

8. Research Question and Objectives

8.1 Primary

Hypocalcemia HD patients with cinacalcet prescription (Cohort 1)

- 8.1.1 To determine the rate of cinacalcet discontinuation following hypocalcemia event
- 8.1.2 To describe prescribing patterns of any treatment intervention (e.g. vitamin D, phosphate binders and cardiovascular disease (CVD) medications) prior to cinacalcet initiation, at time of cinacalcet initiation and after hypocalcemia event
- 8.1.3 To describe time to any treatment intervention and treatment patterns (e.g. vitamin D, phosphate binders and cardiovascular disease (CVD) medications) prior to cinacalcet initiation, at time of cinacalcet initiation and after hypocalcemia event
- 8.1.4 To identify factors associated with changes to any treatment intervention following a hypocalcemic event

8.2 Secondary objectives

HD patients with cinacalcet prescription and serum calcium >8.4 mg/dL at baseline

(Cohort B)

- 8.2.1 To determine the incidence of hypocalcemia in SHPT patients with CKD on HD following cinacalcet initiation
- 8.2.2 To determine the frequency of hypocalcemia events in cinacalcet patients
- 8.2.3 To determine time to first hypocalcemia event
- 8.2.4 To describe characteristics of cinacalcet patients who develop and who do not develop hypocalcemia
- 8.2.5 To identify factors associated with time to hypocalcemia event in cinacalcet patients

Hypocalcemia HD patients who discontinued cinacalcet prescription (Cohort C)

- 8.2.6 To determine time to cinacalcet re-initiation
- 8.2.7 To determine the rate of cinacalcet re-initiation among patients who discontinued cinacalcet following hypocalcemia event
- 8.2.8 To describe factors associated with time to cinacalcet re-initiation event in patients who discontinued cinacalcet following hypocalcemia event
- 8.2.9 To describe treatment patterns (e.g. vitamin D, phosphate binders and CVD medications) at time of hypocalcemia event, at time of discontinuation, and at time of cinacalcet re-initiation
- 8.2.10 To describe the trajectory of PTH, calcium and phosphate values following cinacalcet initiation, following hypocalcemia event, and following cinacalcet re-initiation

8.3 Exploratory

- 8.3.1 To explore the number of HD patients who initiate cinacalcet (i.e. first prescription) with hypocalcemia (*Cohort A*)

HD patients with cinacalcet prescription and serum calcium >8.4 mg/dL at baseline

(Cohort B)

- 8.3.2 To explore the incidence of hypocalcemia events among HD patients with cinacalcet prescription according to PTH levels
- 8.3.3 To explore the frequency of hypocalcemia events among HD patients with cinacalcet prescription according to PTH levels

Hypocalcemia HD patients with cinacalcet prescription (Cohort 1)

- 8.3.4 To explore kinetics of hypocalcemia events in cinacalcet patients with more than one episode of hypocalcemia
- 8.3.5 To explore the impact of hypocalcemia treatment on serum calcium level
- 8.3.6 To explore the impact of hypocalcemia cardiovascular events (CVE) or death

9. Research Methods

9.1 Study Design

A retrospective cohort of chronic kidney disease patients receiving hemodialysis in European Fresenius Medical Care (FMC) facilities will be carried out. The cohort design will allow us to utilize available data to study multiple outcomes (e.g. development of hypocalcemia and changes in treatment strategies, calcium recovery, and reinitiation of cinacalcet among hypocalcemia patients) and provide an opportunity to describe the management of hypocalcemia in the hemodialysis population.

9.2 Setting and Study Population

The source population for this study is the AROii cohort, which comprises of adult subjects presenting at one of 304 participating facilities in 14 European countries (*Czech Republic, France, Hungary, Ireland, Italy, Poland, Portugal, Romania, Russia, Serbia, Slovak Republic, Slovenia, Spain, and United Kingdom*) and Turkey enrolled between 01 January 2007 and 31 December 2009. Out of 10,600 patients enrolled, 1876 patients were still on follow-up by the end of 2014.

AROii, a closed-cohort by design, comprises of chronic (ten or more contiguous dialysis sessions) incident (<183 days since commencing renal replacement therapy (RRT)) haemodialysis patients with no history of renal transplantation or peritoneal dialysis. Data are captured electronically via the FMC European Clinical Database (EuCliD) and supplied on a quarterly basis. By Q4 2014, the AROii study population had accrued over 33,000 person-years of follow-up.

9.2.1.1 Study Period

The study period will be 01 January 2007 to 31 December 2014.

9.2.2 Subject/Patient/Healthcare Professional Eligibility

9.2.2.1 Inclusion/Exclusion Criteria

Inclusion criteria

HD patients in AROii cohort i) aged ≥ 18 , ii) filled a cinacalcet prescription after 01 January 2007, iii) enrolled in AROii for at least 90 days prior to cinacalcet initiation and have at least 90 days follow-up following cinacalcet initiation (*Cohort A*). HD patients who have serum Ca ≥ 8.4 mg/dL at time of cinacalcet initiation will be included in subsequent analyses (*Cohort B*). A sub-set of HD patients who develop hypocalcemia (serum Ca < 8.4 mg/dL) will define *Cohort 1* which will be used to evaluate the primary objectives. HD patients with hypocalcemia who discontinued cinacalcet will be included in further sub-analyses (*Cohort C*).

Exclusion criteria

Patients with i) parathyroidectomy up to and including the first 90 days of follow-up, ii) a prescription for cinacalcet is less than 15 days (2 weeks) with no further prescriptions

9.2.4 Study Follow-up

In this retrospective AROii cohort study, follow-up commenced on the date they initiated a cinacalcet prescription.

- For Cohort 1 (hypocalcemia HD patients with Cinacalcet prescription), follow-up continued for 12 months following development of hypocalcemia.
- For Cohort B (HD patients with Cinacalcet prescription and serum calcium >8.4 mg/dL), continued for 12 months following cinacalcet initiation
- For Cohort C (hypocalcemia HD patients who discontinued cinacalcet prescription), follow-up continued for 12 months following discontinuation of cinacalcet.

9.2.4.1 Censoring

Patients will begin to accrue time at risk from the end of their relevant baseline period until they experienced hypocalcemia (*Cohort B*), discontinued cinacalcet (*Cohort 1*) or reinitiated cinacalcet (*Cohort C*). Patients will also be censored if they died, underwent parathyroidectomy or a renal transplant, or were lost to follow-up during the respective follow-up periods. Patients will be considered lost to follow-up if they left a dialysis facility for any reason and did not return to the same or another FMC facility within 45 days.

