9.3.2.1 Incidence of hypocalcemia

The cumulative incidence of first hypocalcemia event (# of new cases with serum calcium value <8.4 mg/dL) will be calculated overall and stratified by mutually exclusive groups of mild (≥ 8.0 - < 8.4 mg/dL), moderate (≥ 7.5 - < 8.0 mg/dL), and severe (< 7.5 mg/dL).

The time period will be monthly following cinacalcet initiation. Patients are at risk for each specified time period if they have an active supply of cinacalcet and therefore at risk of hypocalcemia. Patients are not at-risk if they do not have an active supply of cinacalcet, died, had a parathyroidectomy or a renal transplant, or was lost to follow-up during the specified time period.

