9.6.2.2 Analysis of the Primary, Secondary and Exploratory Endpoint(s)

9.6.2.3 Primary and secondary objective endpoints

Point estimates and 95% confidence intervals will be derived to determine the rate of hypocalcemia following cinacalcet initiation, rate of cinacalcet discontinuation following hypocalcemia event and rate of cinacalcet re-initiation following discontinuation due to hypocalcemia.

Time to first hypocalcemia event, time to any treatment intervention following hypocalcemia event, and time to cinacalcet re-initiation will be estimated using Kaplan-Meier methods according to baseline calcium levels (i.e. mild, moderate or severe) at baseline.

Cox regression models will be used to identify baseline covariates (Table 2) associated with time to first occurrence of hypocalcemia during the first 12 months of the study, time to any treatment intervention during the 12 months following hypocalcemia event and time to cinacalcet re-initiation during the 12 months following cinacalcet discontinuation. Subjects who do not experience hypocalcemia will be censored (according to 9.2.4.1 criteria). Univariate analysis will be performed. Variables significant at the 0.25 level in univariate analysis will be entered into a multivariate analysis using a stepwise regression technique (significance levels of 0.10 for inclusion/exclusion). Hazard ratios and 95% confidence intervals will be presented.

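### Kaplan-Meier with death, parathyroidectomy and transplant censored modestly overstates the probability of first hypocalcemia and of cinacalcet re-initiation

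*Protocol*

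**What the plan says.** Protocol section 9.2.4.1 sets one censoring rule for Cohorts B, 1 and C: "Patients will also be censored if they died, underwent parathyroidectomy or a renal transplant", and the same sentence treats loss to follow-up in the same way. Loss to follow-up is broad: "Patients will be considered lost to follow-up if they left a dialysis facility for any reason", with no return to the network within 45 days.

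Section 9.6.2.3 names the estimator for time to first hypocalcemia (objective 8.2.3) and for re-initiation (objective 8.2.6): "time to cinacalcet re-initiation will be estimated using Kaplan-Meier methods". The same sentence covers time to any treatment intervention, which is not assessed here.

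Section 9.3.2.1 defines the incidence outcome (objective 8.2.1) as "The cumulative incidence of first hypocalcemia event", counted by month. Patients who have died, been operated on or been transplanted leave the at-risk set, as do patients without active cinacalcet supply. That section names no estimator. No competing-risk estimator appears anywhere in the protocol.

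**The concern.** Kaplan-Meier treats a censored patient as someone who could still have the event later, at the same rate as those who remain. That is reasonable for a patient who moves to another provider. It is not reasonable for a patient who has died, and by the protocol's own at-risk rules it does not fit one whose at-risk period ended with surgery or transplant. With these events censored, 1-KM is the probability in a hypothetical population in which they never happen. It is at least as large as the proportion of actual patients who reach the event.

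The objectives are descriptive and the rationale is to characterise real practice, so the real-world proportion is the quantity wanted. A reader will take the 12-month point of the curve as the share of patients who become hypocalcemic or restart. That error goes in one direction, does not shrink with sample size, and is not reflected in the confidence interval.

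**Working it through.** **The plan's own figures.** Section 9.5 gives a maximum half width of 0.040 for 600 patients. 1.96 x sqrt(0.25/600) = 0.0400, which reproduces. 1245 x 0.47 = 585, in line with about 600.

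**Exit rate of the source cohort.** Section 9.2: "Out of 10,600 patients enrolled, 1876 patients were still on follow-up by the end of 2014", and "the AROii study population had accrued over 33,000 person-years of follow-up".
- Exits for any reason: 10,600 - 1,876 = 8,724.
- Rate: 8,724/33,000 = 0.264 per person-year. This is a ceiling, because the person-years are stated as a minimum.
- Share of patients leaving in one year: 1 - exp(-0.264) = 23%.
- The share due to death, parathyroidectomy or transplant is not given. I assume 50-100%, so the competing hazard d is 0.132 to 0.264 per year.

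**First hypocalcemia (Cohort B).** I take 1-KM = 0.47 at 12 months, using the expected proportion in section 9.5. With a constant hazard, h = -ln(0.53) = 0.635. Section 9.2.2.1 requires 90 days of follow-up after initiation and excludes parathyroidectomy in that period, so no competing event can occur before c = 90/365.25 = 0.246 years:

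CIF = [1 - exp(-hc)] + exp(-hc) x h/(h+d) x [1 - exp(-(h+d)(1-c))]

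- d = 0.264: 0.145 + 0.855 x 0.706 x 0.492 = 0.442, so 1-KM is 2.8 points too high (6% relative).
- d = 0.132: 0.145 + 0.855 x 0.828 x 0.439 = 0.456, so 1-KM is 1.4 points too high (3% relative).

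If 50-70% of the cumulative hypocalcemia hazard falls in the first 90 days, the excess is 1.0-1.8 points at d = 0.264 and 0.5-0.9 points at d = 0.132.

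For comparison, ignoring the 90-day rule gives CIF = h/(h+d) x [1 - exp(-(h+d))] = 41.9-44.3%, an excess of 2.7-5.1 points. The eligibility rule roughly halves the problem in Cohort B.

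**Re-initiation (Cohort C).** The protocol gives no expected value. I assume a 12-month 1-KM of 40%, with 20-70% as the range.

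| Assumption | CIF when 1-KM = 40% | Excess at 40% | Excess over 20-70% |
|---|---|---|---|
| Exits and restarts possible from day 0 | 35.5-37.7% | 2.3-4.5 points | 1.2-6.9 points |
| Neither possible in the first 90 days | 36.6-38.2% | 1.8-3.4 points | 0.9-5.3 points |

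The second row applies if discontinuation is dated at the start of the prescription-free gap of 90 days (section 9.3.1.3). Cohort membership then requires 90 observed days without a prescription. The formula is the one without the 90-day rule, with d replaced by d(1-c) and h kept as the total hazard.

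**The case against.** Much of the case for leaving the plan alone is sound.

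- **The exit rate is not a competing-event rate.** It covers the whole source cohort and includes patients who simply left the network. A reader might infer that the cinacalcet cohorts lose 26% of their patients each year to competing events. The documents do not support that: 0.264 is a rate per person-year, it corresponds to about 23% of patients, and it is not split by cause or by cohort.
- **Cohort B is protected early.** A relative overstatement of 6-12% for hypocalcemia might be inferred by applying the exit rate from day 0. The 90-day rule reduces this to 3-6%, and to less if events come early.
- **Not every frequency objective is affected.** Table 1 defines the re-initiation rate (8.2.7) as a yes/no count of patients. A simple proportion carries no 1-KM bias. For 8.2.1 the problem enters only through the at-risk rule in section 9.3.2.1.
- **Only death strictly precludes both outcomes.** Hypocalcemia is defined by a calcium value and re-initiation by a new prescription. Surgery and transplant end at-risk status by rule, not by the outcome definitions.
- **Stronger bias in sicker patients**, distorting comparisons by severity, might also be inferred. It is plausible, but no figure in the protocol shows it.
- **The Cox models are unaffected.** Censoring competing events is the accepted approach for cause-specific hazards.

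One might add that the Cohort B excess is below the 0.040 half width that the protocol accepts. That comparison is weak. The 0.040 belongs to discontinuation in Cohort 1. Cohort B can hold up to 1,245 patients, for whom the maximum half width is 1.96 x sqrt(0.25/1245) = 0.028, about equal to the upper excess of 2.8 points.

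These points limit the scope and size of the problem. They do not remove it: the protocol fixes both the censoring rule and the estimator, so this is not a detail left open for the SAP.

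**Conclusion.** The point stands, at modest size. Kaplan-Meier under section 9.2.4.1 overstates the real-world probability of first hypocalcemia (8.2.3) and of re-initiation (8.2.6). Monthly risks accumulated over the at-risk set of section 9.3.2.1 share the problem, so the incidence under 8.2.1 is exposed as well. The yes/no re-initiation proportion (8.2.7) and the Cox hazard ratios are not.

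For hypocalcemia the excess is about 1.4-2.8 points on 47%, and less if events cluster early. For re-initiation it is about 2 to 4.5 points on an assumed 40%, and about 1 to 7 points over an assumed 20-70%. All of this rests on constant hazards unless noted, on the source cohort's exit rate applying to the cinacalcet patients, and on 50-100% of exits being competing events. The last two cannot be checked from the protocol. The direction does not depend on them. The objectives concerned are secondary.

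**What to change.** In sections 9.2.4.1 and 9.6.2.3, specify that cumulative incidence of first hypocalcemia and of re-initiation will be estimated with the Aalen-Johansen estimator. Death, parathyroidectomy and renal transplant are the competing events; only loss to follow-up and the end of the 12-month window are censoring. State in section 9.3.2.1 that the cumulative incidence there uses the same estimator. Keep the Cox models and label their hazard ratios cause-specific. It would also help to report the number of each competing event by cohort, so that readers can see how much it matters.

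The cost is a few lines of text and a standard software option. No new data are needed: the present censoring rule already requires the dates of these events, and section 9.4 lists deaths, parathyroidectomy and transplantation among the captured data. The downside is a slightly lower reported incidence.

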9.3 Variables

9.3.1 Exposure Assessment

9.3.1.1 Cinacalcet initiation

Cinacalcet initiation will be defined as the start date of patients' first prescription. If a patient's first prescription duration was less than 15 days (2 weeks) and the gap between the end date of the first prescription to the start date of the second prescription was greater than 15 days then the second prescription will be used to identify treatment initiation (same rules will apply for the second and subsequent prescription)

9.3.1.2 Development of hypocalcemia

Patients who developed hypocalcemia as defined by serum calcium <8.4 mg/dL.

9.3.2 Outcome Assessment

Table 1 summarizes the outcomes to be assessed according to each objective.

Table 1. Outcomes for analysis

Objective	Definition
PRIMARY OBJECTIVES	
Hypocalcemia HD patients with cinacalcet prescription	
- Rate of cinacalcet discontinuation	- Number of patients who discontinue cinacalcet. Discontinuation is defined as the time point beyond which there were ≥ 90 consecutive prescription-free days.
-Cinacalcet prescribing pattern	- No change, dose reduced (relative to dose prior to hypocalcemia), discontinued, Dose increased (relative to dose prior to hypocalcemia)
- Prescribing pattern for any treatment and each of the following drugs: paricalcitol, older AVD, phosphate binder, dialysate calcium and CVD medications	- No change, dose reduced (relative to dose prior to hypocalcemia), discontinued, Dose increased (relative to dose prior to hypocalcemia)
SECONDARY OBJECTIVES	
HD patients with cinacalcet prescription	
- Incidence of hypocalcemia	- First occurrence of a serum calcium (< 8.4 vs. ≥ 8.4 mg/dL) - First occurrence of serum calcium defined by severity: mild (serum calcium ≥ 8.0 - < 8.4 mg/dL), moderate (serum calcium ≥ 7.5 - < 8.0 mg/dL), severe (serum calcium < 7.5 mg/dL)
Hypocalcemia HD patients who discontinued cinacalcet prescription	
- Rate of cinacalcet re-initiation	- Number of patients who re-initiate cinacalcet prescription following discontinuation (yes/no)
- Prescribing pattern for each of the following drugs: cinacalcet, paricalcitol, older AVD, phosphate binder, dialysate calcium and CVD medications	- No change, dose reduced (relative to dose prior to hypocalcemia), discontinued, Dose increased (relative to dose prior to hypocalcemia)
EXPLORATORY OBJECTIVES	
- Incidence of hypocalcemia by PTH	- No. of patients with hypocalcemia according to PTH levels: low (< 10 ng/L or pg/mL), normal (10-65 ng/L or pg/mL) or high (> 65 ng/mL or pg/mL)
- Kinetics of hypocalcemia	- Progressors (subsequent events were more severe than initial events), remitters (subsequent events were less severe than initial events), fluctuators (events ranged in severity with no trend in one direction)
- Changes in calcium level	- Changes in mean or median calcium levels following changes in treatment treatment
- Cardiovascular event	- Any coronary artery event (CVE), cerebrovascular event (CVE), peripheral arterial event (PAE), congestive heart failure event (CHFE), or sudden cardiac event (SCE)

Definitions of specific outcomes are more detailed below.

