in about one-third of patients. Other management strategies included discontinuation or reduction in the dose of cinacalcet in 22% of patients and initiation or up-titration of a calcium-containing phosphate binder in 3% of patients; and there was also an increase in dialysate calcium concentration in 7% of patients. The majority of patients returned to normal calcium (total calcium ≥ 8.4 mg/dL) levels within 90 days following the hypocalcemia event irrespective of whether they continued or discontinued cinacalcet following the hypocalcemia event. However, the generalizability of these US treatment practices for management of hypocalcemia may be limited and cannot be extrapolated to management practices in a European hemodialysis population. It is recognized that patient characteristics and treatment with cinacalcet in Europe and the US differ hence treatment strategies and practices to address calcium reductions are also likely to differ.

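### In Cohort 1 the any-treatment outcome, as listed, leaves out cinacalcet changes, while the cohort's only at-risk rule ends at cinacalcet discontinuation

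*Protocol*

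**What the plan says.** **The composite.** Among the primary outcomes for Cohort 1, Table 1 (Protocol Section 9.3.2) has one row headed "Cinacalcet prescribing pattern" and a second for "Prescribing pattern for any treatment and each of the following drugs: paricalcitol, older AVD, phosphate binder, dialysate calcium and CVD medications". The second row does not name cinacalcet. Objective 8.1.2 reads "To describe prescribing patterns of any treatment intervention (e.g. vitamin D, phosphate binders and cardiovascular disease (CVD) medications" and so on; 8.1.3 gives the same three examples. Both lists are open, and neither names cinacalcet.

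**The at-risk rule.** Section 9.2.4.1 gives one event per cohort at which time at risk ends. After hypocalcemia for Cohort B, it continues: "discontinued cinacalcet (*Cohort 1*) or reinitiated cinacalcet (*Cohort C". Death, parathyroidectomy, transplant and loss to follow-up also censor.

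**The analysis.** Section 9.6.2.3 applies Kaplan-Meier and Cox methods to three endpoints. The one belonging to Cohort 1 is "time to any treatment intervention during the 12 months following hypocalcemia event".

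**The background.** Section 7.1, on the US study that motivates the work, says: "Other management strategies included discontinuation or reduction in the dose of cinacalcet in 22% of patients".

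**The concern.** The protocol asks how clinicians respond to a low calcium. Its own background treats acting on cinacalcet as one of the responses, yet the lists that give content to any treatment intervention do not contain it. The single Cohort 1 at-risk rule was evidently written for the discontinuation endpoint. Carried over to time to any treatment intervention, it ends observation at the moment when some clinicians act.

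Two primary objectives depend on this endpoint: 8.1.3 (time to any intervention) and 8.1.4 (factors associated with changes). Leaving the risk set because cinacalcet was stopped is plausibly related to the severity of the event and to the clinician's readiness to act, so the censoring is plausibly informative. A factor that leads clinicians to act on cinacalcet rather than on other therapies could look unrelated to intervention, or even inversely related to it.

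**Working it through.** **1. The plan's own figure.** Section 9.5: 1245 × 0.47 = 585, stated as approximately 600. The maximum 95% half width is 1.96 × √(0.25/600) = 0.040 (0.0405 at n = 585). Both reproduce. They concern the proportion discontinuing, not this endpoint, and serve here only to supply 600 as a base.

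**2. At-risk rule against analysed endpoint.**

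| Cohort | Time at risk ends at (9.2.4.1) | Time-to-event endpoint (9.6.2.3) | Same event? |
|---|---|---|---|
| B | hypocalcemia | first hypocalcemia | yes |
| 1 | cinacalcet discontinuation | any treatment intervention | no, unless cinacalcet changes count |
| C | cinacalcet re-initiation | cinacalcet re-initiation | yes |

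Only Cohort 1 fails to match.

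**3. What happens to a patient under each reading.**

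| Course after hypocalcemia | Cinacalcet outside the composite | Cinacalcet inside the composite |
|---|---|---|
| Cinacalcet stopped first | leaves risk set without an event; later changes to other therapies unseen | event at discontinuation |
| Cinacalcet dose reduced, nothing else | event-free to 12 months | event at reduction |
| Other therapy changed first | event | event |

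**4. Direction.** Turning a censored time into an event at that same time can only lower the Kaplan-Meier curve. For patients who stop first, the first reading therefore gives less intervention than the second. Patients with a dose reduction alone add non-events in the same direction. For the Cox models, the direction for a given covariate cannot be determined from the documents.

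**5. Illustration of size.** The inputs are US figures cited in Sections 7.1 and 7.2: vitamin D about one-third, calcium-containing binder 3%, dialysate calcium 7%, cinacalcet reduced or stopped 22%, cinacalcet stopped about 17%. They are assumed to share a denominator and to carry over to Cohort 1.

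- Patients meeting discontinuation: 0.17 × 600 = 102. Fewer would leave without an event, because some would have another change first.
- Patients whose only intervention is a cinacalcet change: at most 0.22 × 600 = 132. The lower end is taken as 0, for reasons given under the verdict.
- Let o be the 12-month probability of a non-cinacalcet intervention, between 33.3% (complete overlap) and 33.3 + 3 + 7 = 43.3% (no overlap), and d that of a cinacalcet change. If the two are independent, the wider composite is 1 − (1 − o)(1 − d), a gain of d(1 − o).

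| o | d | Wider composite | Gain (points) |
|---|---|---|---|
| 33.3% | 17% | 44.7% | 11.3 |
| 43.3% | 17% | 53.0% | 9.6 |
| 33.3% | 22% | 48.0% | 14.7 |
| 43.3% | 22% | 55.8% | 12.5 |

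Independence is itself an assumption. Without it, the illustrated gain runs from 0 to 22 points.

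**The case against.** **Exclusion is not stated.** The Table 1 row can be parsed so that the drug list belongs only to the second half of its heading, with any treatment standing apart and wider. The objectives' lists are examples, and Section 9.6.2.4 uses any treatment without limiting it to non-cinacalcet drugs. If cinacalcet changes count, discontinuation is an event and that part of the problem disappears. This stands: exclusion is the natural reading, not an explicit rule. But if inclusion is intended, Table 1 and 8.1 should say so.

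**The Cohort C row proves little.** That row, "Prescribing pattern for each of the following drugs: cinacalcet, paricalcitol, older AVD, phosphate binder, dialysate calcium and CVD medications", does name cinacalcet, and a reader might infer a deliberate omission for Cohort 1. Cohort C has no separate cinacalcet row, so layout alone could explain the difference.

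**Section 9.6.2.3 does not apply the rule to this endpoint.** A reader might take its censoring sentence as doing so. That sentence concerns subjects without hypocalcemia, and every Cohort 1 patient has had it. The rule reaches this endpoint only because it is the sole Cohort 1 rule given.

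**These patients are not lost.** Discontinuation and cinacalcet dose change are primary outcomes in their own right, and discontinuation is the basis of the sample size. This stands, and it limits the scope of the problem.

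**Censoring at discontinuation gives a cause-specific hazard.** That is a recognised target, but the protocol does not claim it. Nor does stopping cinacalcet prevent a later change in vitamin D, binder or dialysate, so it is not a natural end of observation for those therapies.

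**Detail for the SAP.** Endpoint-specific censoring rules often belong there, and only the protocol is at hand. Here, however, the protocol itself fixes a list and a rule that do not fit the endpoint it analyses.

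**Conclusion.** The point holds on the natural reading of the text. The any-treatment composite omits a response that Section 7.1 counts as management, and the one Cohort 1 at-risk rule does not match the one Cohort 1 time-to-event endpoint. As written, the composite understates intervention and the predictors sought under 8.1.4 can be distorted. The effect is confined to the composite, its time-to-event analysis and 8.1.4.

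Its size cannot be fixed from the documents. A reader might infer a floor: the US non-cinacalcet strategies sum to at most 43.3%, the mildest band had 48.6% treated, so at least 5.3 points must be cinacalcet alone. That does not follow:

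- Section 7.1 does not present the US list as complete.
- The US items are additions and up-titrations, whereas Table 1 counts changes in either direction, all phosphate binders and CVD medications. The composite here is broader than 43.3% implies.
- The drug percentages carry no severity band or stated common denominator, so they cannot be set against one band's total.
- Section 7.1 itself says that US practice cannot be extrapolated to Europe.

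The CVD medications and two-way changes also mean that the gains in the working are illustrations, not predictions.

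**What to change.** - **Table 1, 8.1.3 and 8.1.4:** count cinacalcet dose reduction or discontinuation after hypocalcemia as an event in any treatment intervention, dated to the change. Show the non-cinacalcet composite and each component separately.
- **Section 9.2.4.1:** give each Cohort 1 outcome its own end-of-risk rule. Discontinuation is the event for the discontinuation endpoint, an event for any treatment intervention, and not a censoring event for the other therapies.
- **Separate drafting slip:** 8.1.2 and 8.1.3 nearly duplicate each other, and the cinacalcet prescribing objective (number 2 in the summary table) is missing from 8.1. Reconcile these.

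The cost is wording. Section 9.4 already lists prescription dose, start and end dates among the data captured. The downside is a composite that is higher and less specific to add-on therapy, which is why the components should be shown beside it.
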